**Table 5-1: Date of Progression or Censoring for DOR**

| Situation                    | Date of progression or censoring                                   | Outcome |
|------------------------------|--|---------|
| Disease progression or death | Date of death or date of disease assessment (planned or unplanned) | Event   |

|  |  |          |
|--|--|----------|
|  | showing disease progression, whichever occurs first                          |          |
| Subsequent anticancer treatment started before the first disease progression | Date of last disease assessment prior to the subsequent anticancer treatment | Censored |
| Alive and without disease progression on or before the EOS visit             | Date of last disease assessment  | Censored |

- Progression-Free Survival (PFS) defined as time from first dose of study drug to date of documented disease progression or death due to any cause. PFS will be calculated as follows:

$$\text{PFS (months)} = (\text{Event/Censoring Date} - \text{Date of the First Dose} + 1) / 30.4375$$

PFS will be right-censored for subjects who met one or more of the following conditions:

- subsequent anticancer therapy in the absence of documented disease progression
- alive and without documented disease progression on or before the EOS visit

If a subject meets more than one of these conditions, then the scenario that occurs first will be used to determine PFS. The event or censoring date will be determined based on the conventions listed in Table 5-2:

**Table 5-2: Date of Progression or Censoring for PFS**

| Situation  | Date of progression or censoring   | Outcome  |
|--|--|----------|
|  |  |          |
| Death or disease progression   | Date of death or first disease assessment (planned or unplanned) showing disease progression, whichever occurs first | Event    |
| No evaluable disease assessments   | Date of the first dose   | Censored |
| Subsequent anticancer treatment started before the first documented disease progression or death | Date of last disease assessment prior to the subsequent anticancer treatment   | Censored |
| Alive and without disease progression on or before EOS visit                                     | Date of last disease assessment  | Censored |

## 5.2 Safety Endpoints

The protocol-defined safety endpoints are the incidence of AEs and the incidence of DLTs. The AEs will be coded using MedDRA version 24.1 and be graded by NCI CTCAE v5.0.

Standard safety assessments for oncology trials such as SAEs, clinical laboratory safety tests including hematology (complete blood count [CBC]), serum chemistry, physical examination, vital signs, Eastern Cooperative Oncology Group (ECOG) performance status, and 12-lead electrocardiogram (ECG) will be conducted and summarized.

### **5.3 Pharmacokinetics of Voruciclib in Monotherapy as well as Voruciclib and Venetoclax in Combination Therapy**

In monotherapy, plasma concentration of voruciclib will be assayed pre- and post-dose of voruciclib as detailed in Section 9.14.1 in the protocol. In combination therapy, the pharmacokinetics of both voruciclib and venetoclax will be assayed as detailed in Section 9.14.2 in the protocol.

### **5.4 Pharmacodynamics of Voruciclib and Voruciclib + Venetoclax**

Blood will be collected for determination of the effect of voruciclib monotherapy and the combination of voruciclib + venetoclax on biomarkers, as detailed in Section 9.15 in the protocol.

### **5.5 Exploratory Endpoints**

- Effects on biomarkers and functional activities of proteins in the apoptotic pathway
- Correlations of anti-tumor activity and baseline tumor characteristics

## **6. ANALYSIS POPULATION**

### **6.1 Safety Evaluable Set**

The Safety Evaluable Set will consist of all enrolled subjects who received any dose of study drug. Analyses pertinent to safety will be conducted on the Safety Evaluable Set.

### **6.2 DLT Evaluable Set**

The DLT Evaluable Set will comprise all subjects in the Safety Evaluable Set who completed the first cycle of treatment (defined as taking at least 75% of the prescribed dose during Cycle 1; for Cohort 12, subjects must receive 100% of Cycle 1 doses (i.e., all 6 doses)) or experienced a DLT during the first cycle of treatment. Subjects who discontinue study therapy prior to completing Cycle 1 (Day 28) for reasons other than the development of a DLT will be replaced. Also, subjects with no DLT who fail to take at least 75% of the planned Cycle 1 voruciclib dose will be replaced; for Cohort 12, subjects with no DLT who fail to receive 100% of Cycle 1 voruciclib doses will be replaced.

The DLT rate will be computed based on subjects in the DLT Evaluable Set.

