4.12. Subject Replacement

Subjects who discontinue study therapy prior to completing Cycle 1 (Day 28) for reasons other than the development of a DLT will be replaced. Subjects who miss one or more doses for reasons other than DLT, must receive at least 75% of the total planned voruciclib dose in Cycle 1 to be assessed for DLT. Subjects with no DLT who fail to receive at least 75% of the planned Cycle 1 voruciclib dose will be replaced.

For Cohort 12, subjects must receive 100% of Cycle 1 doses (i.e., all 6 doses) to be DLT evaluable; subjects with no DLT who fail to receive 100% of Cycle 1 voruciclib doses will be replaced.

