5. VORUCICLIB ADMINISTRATION

5.1. Preparation and Administration of Voruciclib

Voruciclib is provided as 50 mg and 100 mg capsules or tablets (requiring no preparation prior to administration) and is dosed on a milligram (mg) basis with no adjustment in dosing based on subject weight. It is recommended that voruciclib be taken in the morning. Voruciclib is to be administered orally once a day on dosing days.

- Monotherapy cohorts: voruciclib is to be taken on an empty stomach at least 1 hour prior to food or 2 hours after food at the same time each day.
- Combination voruciclib + venetoclax cohorts: subjects should take venetoclax with a meal and water, and then take voruciclib (malonate salt tablets) at least 2 hours later (e.g., meal completed at 8 a.m. with venetoclax, dose of voruciclib taken after 10:00 a.m.).

Note that voruciclib is only to be taken on dosing days in the monotherapy IS regimens (i.e., on Days 1 through 14 of the 28-day cycle on the IS_{2w,2w}, and on Days 1 through 7 only in the 28-day cycle on the IS_{1w,3w}). Dosing days for voruciclib when given in combination with venetoclax are defined in [Table 5](#) for IS_{2w,2w}, and in [Table 6](#) for IS_{3w,1w}.

If a dose is missed it may be taken up to 12 hours after the specified time. After 12 hours the dose should be omitted. If a subject vomits after taking voruciclib, no replacement dose will be given.

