10.3.2. Analysis Populations

The Safety population is defined as subjects who receive at least one dose of study drug(s).

The DLT evaluable population includes subjects in dose escalation cohorts who complete the first cycle of treatment with at least 75% of study drug compliance or experience a DLT during the first cycle (28 days) of treatment.

The Efficacy evaluable population is defined as subjects who complete the first scheduled post-baseline efficacy evaluation (scheduled on C3D1 for B-cell lymphoma subjects and C2D1 for AML subjects) or develop progression of disease or death prior to the first scheduled post-baseline efficacy.

The PK population will include all subjects who receive at least 1 dose of voruciclib or venetoclax and have at least 1 non-missing post-dose concentration value.

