### **3.1.4 Subject Replacement**

Subjects who discontinue study therapy prior to completing Cycle 1 (Day 28) for reasons other than the development of a DLT will be replaced. Subjects who miss one or more doses for reasons other than a DLT, must receive at least 75% of the total planned dose in Cycle 1 to be assessed for a DLT. Subjects with no DLT who fail to receive at least 75% of the planned Cycle 1 voruciclib dose will be replaced.

For Cohort 12, subjects must receive 100% of Cycle 1 doses (i.e., all 6 doses) to be DLT evaluable; subjects with no DLT who fail to receive 100% of Cycle 1 voruciclib doses will be replaced.

The data collected from subjects being replaced will be analyzed according to the analysis population(s) they belong to. Analysis population(s) are defined in Chapter 6.

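### SAP 6.2 equates completing Cycle 1 with taking 75% of the dose, so a DLT-free subject who stops therapy before Day 28 can enter the DLT-rate denominator although the same section has that subject replaced

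*SAP*

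**What the plan says.** **SAP 6.2.** A subject belongs to the DLT Evaluable Set after a Cycle 1 DLT, or having "completed the first cycle of treatment (defined as taking at least 75% of the prescribed dose during Cycle 1". For Cohort 12 the threshold is higher: "subjects must receive 100% of Cycle 1 doses (i.e., all 6 doses". The section then says: "The DLT rate will be computed based on subjects in the DLT Evaluable Set".

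**Protocol 10.3.2.** The DLT population is made up of escalation subjects who "complete the first cycle of treatment with at least 75% of study drug compliance or experience a DLT". Here the 75% is added to completing the cycle; it does not define it.

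**Protocol 4.12.** The rule is "Subjects who discontinue study therapy prior to completing Cycle 1 (Day 28) for reasons other than the development of a DLT will be replaced". Separately, a subject without a DLT must have had at least 75% of planned Cycle 1 voruciclib (all six doses in Cohort 12). SAP 3.1.4 and SAP 6.2 itself carry the same Day 28 replacement rule.

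**SAP 3.1.4.** On subjects who have been replaced: "The data collected from subjects being replaced will be analyzed according to the analysis population(s) they belong to".

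**SAP 10** states that nothing has changed from the protocol's analyses.

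**The concern.** The bracket in SAP 6.2 turns two conditions into one. Completing the cycle becomes a statement about dose taken, with no reference to time. Voruciclib is given early in the cycle on all the intermittent schedules, so the dose condition can be met well before the 28-day window closes. The replacement sentence that follows uses Day 28, so one section holds two meanings of completion.

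Replacement does not settle the matter. SAP 3.1.4 keeps a replaced subject in any population whose definition he or she meets, and no sentence takes replaced subjects out of the DLT Evaluable Set. A programmer who follows the bracket would count both the early leaver and the replacement as DLT-free.

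DLT incidence is part of the primary endpoint (Protocol 10.2), and cohorts have three to six evaluable subjects, so one misplaced subject is visible in the rate. The early leaver has not received the full Cycle 1 regimen. In combination cohorts that includes all or part of the Days 22–28 venetoclax segment. The leaver may also not be fully observed, if he or she withdraws, dies or starts new anti-cancer therapy.

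**Working it through.** **Step 1. Reproduce the plan's own count.** SAP 6.2 gives one figure, six doses in Cohort 12. The Cycle 1 dosing days are 3, 5, 7, 9, 11 and 13, which is six. It reproduces.

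**Step 2. Day on which the threshold is met.** Dosing days come from Protocol 5.1 for monotherapy intermittent schedules (for IS2w,2w, "on Days 1 through 14 of the 28-day cycle"), Protocol 4.3.2.1 for combination cohorts, and the synopsis rationale for Amendment 7 for continuous dosing. With n planned Cycle 1 voruciclib doses, the number needed is 0.75 × n rounded up (n itself in Cohort 12). The threshold day is the day of that dose, assuming none is missed.

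| Schedule | Dosing days | n | Needed | Day met |
|---|---|---|---|---|
| IS1w,3w, monotherapy (Cohorts 9–11) | 1–7 | 7 | 5.25 → 6 | 6 |
| IS2w,2w, monotherapy (6–8) | 1–14 | 14 | 10.5 → 11 | 11 |
| IS2w,2w, combination (13–19) | 3–14 | 12 | 9 | 11 |
| Cohort 12 | 3, 5, …, 13 | 6 | 6 | 13 |
| IS3w,1w, combination (protocol 21–25; SAP Cohort 20) | 3–21 | 19 | 14.25 → 15 | 17 |
| Continuous (1–5) | 1–28 | 28 | 21 | 21 |

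Every schedule meets its threshold before Day 28. In the combination cohorts it is met before Day 22, when venetoclax goes to 400 mg.

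**Step 3. A concrete leaver.** Take a subject who stops on Day 12 before that day's dose. Doses taken are 9/12 = 75.0% (combination IS2w,2w), 11/14 = 78.6% (monotherapy IS2w,2w) and 7/7 (IS1w,3w), so the subject qualifies. On the other schedules the subject does not: 11/28 = 39.3% (continuous), 9/19 = 47.4% (IS3w,1w) and 5/6 = 83.3% against a required 100% (Cohort 12). There the same problem starts later.

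**Step 4. Which drug?** The bracket does not name it. Protocol 4.12 and the last replacement sentence of SAP 6.2 point to voruciclib. If venetoclax milligrams were meant, the Cycle 1 total is 100 + 20 × 200 + 7 × 400 = 6900 mg and 75% is 5175 mg. The running total is 4100 mg at Day 21, 4900 mg at Day 23 and 5300 mg at Day 24. The threshold falls on Day 24, still short of Day 28. The Day 12 subject would then not qualify (2100/6900 = 30.4%), but the gap in the definition would remain.

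**Step 5. Effect on the rate.** With x DLTs in six fully evaluable subjects and one early leaver added, x/6 becomes x/7.

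- x = 1: 16.7% becomes 14.3%.
- x = 2: 33.3% becomes 28.6%.
- x = 0: 0% either way.

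**The case against.** **Observation does not stop with treatment.** Adverse events are captured until 30 days after the last dose or the start of new anti-cancer therapy (SAP 8.7.2; Protocol 9.5), and the End of Study visit is 30 days after the last dose (Protocol 8.7). A subject last dosed on Day 11 would normally be followed to about Day 41. A reader might infer that such a subject is unobserved for the last 17 days. The documents do not support that: it happens only after withdrawal, death or new therapy. What stands is incomplete exposure, and incomplete observation for some.

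**Toxicity leavers are mostly caught.** Stopping study drug in Cycle 1 for an adverse event clearly unrelated to disease or an extraneous cause is itself a DLT (Protocol 4.4). The affected subjects are mainly those who leave for progression or withdrawal. This narrows the bias but does not remove it, and SAP 3.1.1 expects departures of this kind.

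**Dose decisions rest on counts.** A reader might infer that escalation is made unsafe, and might compute the chance of a false 0/3 when one subject is only partly observed. The documents do not support that use. SAP 3.1.1 follows subjects for 28 days and, where a fourth is enrolled, closes the DLT period once three have completed 28 days without a DLT. The leaver is replaced, the Study Review Committee must approve escalation, and the MTD is set by fewer than two DLTs in six. Adding a DLT-free subject to a reporting denominator removes no DLT.

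**The effect may be nil in some cohorts.** Protocol 4.3.2 reports no DLTs on combination IS2w,2w from 50 mg QOD to 250 mg QD, so the estimate there is 0% with either denominator. The two DLTs described under continuous 100 mg dosing arose where the threshold falls only on Day 21.

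**The bracket can be read kindly.** Since SAP 6.2 also mentions Day 28 and orders replacement, a programmer could treat replaced subjects as non-evaluable. The sample-size allowance in SAP 4 for non-evaluability after not completing Cycle 1 suggests that this was the intent. But the written definition says otherwise, and an analysis set should not depend on which sentence is followed.

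**Conclusion.** The definition in SAP 6.2 departs from Protocol 4.12 and 10.3.2, conflicts with its own replacement sentence, and is not declared as a change. Followed literally, it admits DLT-free subjects who stopped as early as Day 6 to Day 21, depending on schedule, and nothing in the SAP removes them.

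The consequence is confined to the reported DLT rate, which can be biased downward. With one such subject beside six evaluable ones, the drop is from 16.7% to 14.3%, or from 33.3% to 28.6%. This rests on the literal reading of the bracket, on voruciclib being the drug meant, on no missed doses, and on at least one subject leaving in that interval without a DLT. How many did so is not in the documents.

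The point does not extend to escalation or the MTD. Nor is a Day 12 leaver admitted on every schedule; that example holds for IS2w,2w and IS1w,3w only. It is a stated rule that can give the wrong rate in a primary safety result, and it should be corrected before database lock.

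**What to change.** In SAP 6.2, replace the bracket with both conditions. A subject without a DLT is evaluable only if he or she completed Cycle 1 through Day 28 **and** took at least 75% of planned Cycle 1 voruciclib (100% in Cohort 12), as in Protocol 4.12 and 10.3.2. Name voruciclib explicitly.

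Add to SAP 6.2 or 3.1.4 that subjects replaced for DLT evaluation are outside the DLT-rate denominator. List them separately with days on treatment and days observed, so that nothing seen in them is lost.

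The cost is a sentence or two of SAP text, one extra programmed condition and one listing. No new data are needed and study conduct does not change. The downside is a slightly smaller DLT denominator.

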### **6.3 Efficacy Evaluable Set**

The Efficacy Evaluable Set is defined as subjects who complete the first scheduled post-baseline efficacy evaluation (scheduled on C3D1 for B-cell lymphoma subjects and C2D1 for AML subjects) or develop progression of disease or death prior to the first scheduled post-baseline efficacy. The Efficacy Evaluable Set will be utilized for the analyses of efficacy.

## 6.4 Pharmacokinetics (PK) Set

The PK Set will include all subjects who receive at least 1 dose of voruciclib or venetoclax and have at least 1 non-missing post-dose concentration value.

# 7. GENERAL STATISTICAL CONSIDERATIONS

## 7.1 Definition of Study Day

Study day will be calculated in reference to the first dose date of study drug as follows:

- Assessment/event date – first dose date of study drug + 1, if assessment/event date is on or after the first dose date;
- Assessment/event date – first dose date of study drug, if assessment/event date is before the first dose date.

Under the convention specified above, there will be no Study Day 0.

## 7.2 Baseline Definition

Baseline value for any given parameter is defined as the last assessment obtained prior to the first dose of study drug.

## 7.3 Unscheduled Visits

In general, by-visit summaries will be presented by the scheduled visits (visit number and corresponding visit name of planned clinical encounter). Visit windowing will not be used for handling unscheduled visits. Although unscheduled visits will not be included in by-visit summaries, they will be presented in data listings and will contribute to the derivation of best or worst-case values where required.

## 7.4 Handling of Missing Data

Missing/Partial Dates:

- In cases of incomplete dates (e.g., AE and concomitant medications), the missing components(s) will be assumed as the most conservative value possible. The detailed methods for handling conventions for treatment-emergent adverse events and concomitant medications derivations are specified below.

|  | Missing | Imputation | Exception   |
|--|---------|------------|---|
| Start date
(AE, concomitant medication) | Day     | 01         | Default to Study Day 1 if an event starts the same year and month as Study Day 1 ( and end date is after first dose of IP or conmed/AE is ongoing/not resolved ) |

|  |           |                       |  |
|--|-----------|-----------------------|--|
|  | Day/Month | 01JAN                 | Default to Study Day 1 if an event starts the same year as Day1 ( and end date is after first dose of IP or conmed/AE is ongoing/not resolved )   |
| Stop date
(concomitant medication only ) | Day       | Last day of the month | Default to the End of Study Date or the primary analysis cut-off date for ongoing subjects if the concomitant medication stops the same year and month as the End of Study Date or primary analysis cut-off date for ongoing subjects respectively |
|  | Day/Month | 31DEC                 | Default to the End of Study Date or the primary analysis cut-off date (for ongoing subjects) if the concomitant medication stops the same year as the End of Study Date or primary analysis cut-off date for ongoing subjects respectively         |

- Time from initial diagnosis (months) is calculated as (date of first dose of study drug - date of initial diagnosis + 1)/ 30.4375. If the month and year of the diagnosis are provided but the day is missing, the missing day is imputed as 01. If only the year is provided, then the missing month and day are imputed as Jan 01 for the calculation. If year is missing, put the date to missing.
- Actual data values as they appear in the original case report forms (CRFs) will be presented in the data listings.

Other Missing Values: Missing values for other individual data points will remain as missing unless otherwise specified. Missing values will not be assumed/imputed and only observed values will be used in data analyses and presentations unless otherwise stated.

## 7.5 Handling of Data after Discontinuation of Treatment

If the subjects were not withdrawn from the study, the safety data collected after discontinuation of treatment will be reported unless specified otherwise, and AEs will be followed per protocol Section 6.

## 7.6 Handling of Data from Subjects Undergone Dose Modifications

Data from all enrolled subjects will be reported by the original cohort assignment at enrollment unless otherwise specified. For subjects who underwent dose modifications, results will be reported based on the initial dose level.

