In Amendment 11, subsequent to determination of the safe and mBED of voruciclib monotherapy in AML subjects, the combination of voruciclib with venetoclax will be evaluated in subjects with relapsed and/or refractory AML (see rationale provided below).

The combination cohorts, beginning at Cohort 12 dose level of voruciclib in combination with venetoclax on an IS_{2w,2w} dosing schedule, will be enrolled as follows:

- Cohort 12: 50 mg once every other day (QOD), administered IS_{2w,2w} + venetoclax administered QD × 28 days
- Cohort 13: 50 mg QD, administered IS_{2w,2w} + venetoclax administered QD × 28 days
- Cohort 14: 100 mg QD, administered IS_{2w,2w} + venetoclax administered QD × 28 days
- Cohort 15: 150 mg QD, administered IS_{2w,2w} + venetoclax administered QD × 28 days
- Cohort 16: 200 mg QD, administered IS_{2w,2w} + venetoclax administered QD × 28 days
- Cohort 17: 250 mg QD, administered IS_{2w,2w} + venetoclax administered QD × 28 days
- Cohort 18: 300 mg QD, administered IS_{2w,2w} + venetoclax administered QD × 28 days
- Cohort 19: 350 mg QD, administered IS_{2w,2w} + venetoclax administered QD × 28 days

Dose escalation to the next cohort will be reviewed by the SRC after 3 subjects have completed 1 cycle with no reported DLTs, or after 6 subjects have completed 1 cycle with no more than 1 DLT. (DLT criteria defined below.) Escalation to a subsequent cohort will depend on demonstrated safety and tolerability within a cohort and with the approval of the SRC.

If the next dose level in the AML combination cohort has been declared safe by the SRC, subjects enrolled at a lower dose level may have their dose escalated to the next dose level after completing Cycle 1 without a DLT (intra-subject dose escalation). For example, a subject with AML enrolled in Cohort 13 (50 mg IS_{2w,2w}) may have the dose increased to 100 mg in Cycle 2 if the dose of 100 mg IS_{2w,2w} was deemed safe in Cohort 14 by the SRC.

Dose escalation proceeds until a real-time assessment of clinical and PK parameters by the SRC establishes the safe and mBED for voruciclib in combination with venetoclax. More specifically, a voruciclib dose in combination with venetoclax that meets the following criteria:

- DLT not to exceed 1 in 6 subjects, overall response rate (ORR) ≥30%, as compared to historical ORR of 19% with 400-800 mg venetoclax alone in relapsed/refractory AML ([Konopleva 2016](#)), and

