A Phase 2 study of venetoclax monotherapy in 32 patients with AML (30 with relapsed and/or refractory; 2 newly diagnosed), demonstrated a 19% response rate (2 CR and 4 complete remissions with incomplete hematologic recovery [CRi]) with a median duration of response (DOR) of 48 days. Venetoclax was generally tolerated up to doses of 1200 mg daily (Konopleva 2016). In another study, venetoclax in combination with azacitidine or decitabine in 57 previously untreated elderly AML patients was administered at doses up to 1200 mg. No dose-limiting toxicities (DLTs) were observed, but subjects at the 1200 mg dose had frequent dose reductions due to gastrointestinal (GI) events. Overall, a 61% remission rate was obtained with 14/57 CR and 21/57 CRi (DiNardo 2018).

These data demonstrate that targeted therapy specific for the apoptotic pathway can have significant clinical benefit for patients with both B-cell malignancies and AML. However, despite high response rates, patients are not cured by currently approved therapy and will generally experience disease progression, indicating the need for development of new agents with a complementary mechanism of action that either alone or in combination with venetoclax or other agents enhance disease clearance and circumvent disease resistance.

Myeloid cell leukemia protein 1 (Mcl-1) is a member of the Bcl-2 anti-apoptotic, pro-survival family of molecules that are commonly over-expressed in B-cell malignancies and AML. Overexpression of Mcl-1 is associated with poor prognosis and resistance to therapy. Mcl-1 is not inhibited by venetoclax, which is specific for Bcl-2, and increased expression of Mcl-1 can be a mechanism of resistance for venetoclax therapy. Acquired resistance of lymphoma cell lines to Bcl-2 inhibition in vitro has been shown to involve transcriptional upregulation of Mcl-1 (Yecies 2010). Additionally, non-clinical studies have also demonstrated the ability of Mcl-1 to render AML cells resistant to Bcl-2 targeted agents, and have demonstrated synergy in AML models between agents targeting Bcl-2 with those targeting Mcl-1 expression including cyclin-dependent kinase 9 (CDK9) inhibitors (Pan 2015, Bogenberger 2017, Luedtke 2017).

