Only the tablet formulation containing the voruciclib malonate salt will be used in the voruciclib plus venetoclax combination group.

Table 3: Dose Cohorts with Combination Voruciclib + Venetoclax (Amendment 11)

Cohort Dose Level	Doses and Schedule
12	voruciclib 50 mg QOD, administered IS _{2w,2w} + venetoclax administered QD × 28 days
13	voruciclib 50 mg QD, administered IS _{2w,2w} + venetoclax administered QD × 28 days
14	voruciclib 100 mg QD, administered IS _{2w,2w} + venetoclax administered QD × 28 days
15	voruciclib 150 mg QD, administered IS _{2w,2w} + venetoclax administered QD × 28 days
16	voruciclib 200 mg QD, administered IS _{2w,2w} + venetoclax administered QD × 28 days
17	voruciclib 250 mg QD, administered IS _{2w,2w} + venetoclax administered QD × 28 days
18	voruciclib 300 mg QD, administered IS _{2w,2w} + venetoclax administered QD × 28 days
19	voruciclib 350 mg QD, administered IS _{2w,2w} + venetoclax administered QD × 28 days

Abbreviation: QOD = once every other day

At the completion of the DLT period for each cohort, decisions to escalate in subsequent cohorts will be guided by SRC review of all available safety data, PK and PD data.

For Cohort 12, the dosing of voruciclib will be Days 3, 5, 7, 9, 11, and 13 of Cycle 1, and Days 1, 3, 5, 7, 9, 11, and 13 of Cycle 2 and beyond.

Dose escalation to the next cohort will be initiated after 3 subjects have completed 1 cycle with no reported DLTs, or after 6 subjects have completed 1 cycle with no more than 1 DLT (as defined in [Section 4.4](#)) and with the approval of the SRC after review of safety from the cohort under review.

Intra-patient dose escalation to the next dose in Cycle 2 or later cycle is allowed at the discretion of the investigator and after consultation with the Sponsor if the next dose level has been declared safe by the SRC. More specifically, a subject enrolled at a dose level X may have their dose escalated to the next dose level X + 1 after completing Cycle 1 without a DLT.

Dose escalation proceeds until assessment of clinical and PK parameters by the SRC establishes the safe BED for voruciclib in combination with venetoclax. More specifically, a voruciclib dose in combination with venetoclax that meets the following criteria:

- DLT not to exceed 1 in 6 patients, overall response rate (ORR) $\geq 30\%$, as compared to historical ORR of 19% with 400-800 mg venetoclax alone in relapsed/refractory AML ([Konopleva 2016](#)), and

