**Table 3-3 Cohorts with Combination Voruciclib + Venetoclax in Amendment 12**

| Cohort Dose Level | Doses and Schedule   |
|--------------------------|---|
| 12                       | voruciclib 50 mg QOD, administered IS 2w,2w + venetoclax administered QD × 28 days |
| 13                       | voruciclib 50 mg QD, administered IS 2w,2w + venetoclax administered QD × 28 days  |
| 14                       | voruciclib 100 mg QD, administered IS 2w,2w + venetoclax administered QD × 28 days |
| 15                       | voruciclib 150 mg QD, administered IS 2w,2w + venetoclax administered QD × 28 days |
| 16                       | voruciclib 200 mg QD, administered IS 2w,2w + venetoclax administered QD × 28 days |
| 17                       | voruciclib 250 mg QD, administered IS 2w,2w + venetoclax administered QD × 28 days |
| 18                       | voruciclib 300 mg QD, administered IS 2w,2w + venetoclax administered QD × 28 days |
| 19                       | voruciclib 350 mg QD, administered IS 2w,2w + venetoclax administered QD × 28 days |
| 20                       | voruciclib 150 mg QD, administered IS 3w,1w + venetoclax administered QD × 28 days |

Dose escalation proceeds until a real-time assessment of clinical and PK parameters by the SRC establishes the safe and mBED for voruciclib in combination with venetoclax. More specifically, a voruciclib dose in combination with venetoclax that meets the following criteria:

- DLT not to exceed 1 in 6 subjects, overall response rate (ORR)  $\geq 30\%$ , as compared to historical ORR of 19% with 400-800 mg venetoclax alone in relapsed/refractory AML, and
- Trough plasma concentration of 1 to 1.5  $\mu\text{M}$ , concentrations shown to be synergistic in combination with venetoclax in preclinical models.

Once the safe and mBED of voruciclib in combination with venetoclax is identified by the SRC, which could be a dose less than 350 mg, dose escalation will stop. The subjects still actively dosing in the prior cohort may have their dose escalated to the next dose level after completing Cycle 1 (intra subject dose escalation). Subjects may continue to receive voruciclib plus venetoclax while there is evidence of clinical benefit (partial remission [PR] or better) by the end of Cycle 6 and acceptable toxicity as judged by the Investigator.

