## 7.7 Presentation of Efficacy and Safety Results

Analytical results of efficacy will be reported overall and by tumor type (AML and B-cell malignancies) as well as by treatment regimen (monotherapy and combination therapy) as applicable, whereas safety results will be reported overall and by dose cohort, unless otherwise specified.

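### The combination mBED needs ORR ≥30% at one dose on one schedule, but the SAP summarises response only pooled over doses and schedules and assigns cohort results to the starting dose

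*SAP*

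**What the plan says.** Identifying the safe dose and mBED of the combination is a primary objective (Protocol 2.1, SAP 2.1). SAP 3.1.1 makes this a property of a dose: "More specifically, a voruciclib dose in combination with venetoclax that meets the following criteria", namely DLT in no more than 1 of 6, ORR of at least 30% compared with 19% for venetoclax alone, and a trough of 1 to 1.5 µM. Protocol 4.3.2 gives the same criteria and carries the mBED definition over to IS3w,1w. Protocol 4.5 expects an mBED on each of the two schedules.

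The decision belongs to the SRC: "Dose escalation proceeds until a real-time assessment of clinical and PK parameters by the SRC establishes the safe and mBED".

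For reporting, SAP 7.7 states: "Analytical results of efficacy will be reported overall and by tumor type (AML and B-cell malignancies) as well as by treatment regimen", where regimen means monotherapy or combination. The same sentence has safety reported by dose cohort. SAP 8.6.2.1 (ORR) and 8.6.2.2 (DOR, PFS) repeat the efficacy groupings without dose or schedule, and Protocol 10.6 adds no dose-level ORR.

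On dose changes, Protocol 4.3.2 says "a subject enrolled at a dose level X may have their dose escalated to the next dose level" after a DLT-free Cycle 1, provided that level has been declared safe. SAP 7.6 says: "For subjects who underwent dose modifications, results will be reported based on the initial dose level".

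**The concern.** The activity part of the mBED definition is an ORR at a given dose, and the plan does not estimate that quantity. The combination ORR row merges every level from 50 mg every other day to 350 mg daily, on both schedules. A reader of the planned tables could not tell whether the chosen dose met the 30% criterion or how the doses around it performed.

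The starting-dose rule raises a second issue. SAP 8.7.2 tabulates adverse events by dose cohort, and SAP 3.1.2 bases the mBED on tolerability over two or more cycles, which is when within-subject increases take place. Toxicity that first appears at the higher dose is then shown under the lower one. Cycle 1 DLTs are protected: SAP 3.1.1 excludes subjects whose dose was increased from DLT assessment at the higher level. Later adverse events have no such protection, and neither would responses once ORR is split by cohort. For a minimum effective dose, crediting a later response to the starting dose errs in one direction, towards too low a dose.

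**Working it through.** **1. Benchmark.** Protocol 1 reports 2 CR plus 4 CRi among 32 patients: (2 + 4)/32 = 18.75%, which rounds to the stated 19%. The exact (Clopper-Pearson) 95% interval is 7.2% to 36.4%, so 30% lies inside the benchmark's own uncertainty. The documents attach no error rate, power or minimum sample size to the 30% criterion, so there is no design figure to reproduce.

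**2. What is pooled.** Combination levels are Cohorts 12–19 (8) and 21–25 (5): 8 + 5 = 13 dose-schedule cells reported as one combination ORR.

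**3. Attribution.** In a pooled ORR the starting-dose rule changes nothing, because a responder counts once wherever assigned. In a by-cohort table it matters: ORR uses best overall response (SAP 5.1.2) and marrow is assessed each cycle until CR or CRi (Protocol Appendix 3). With one response at dose X and a second first reached at X+1, cohort X goes from 1/6 = 16.7% (below 30%) to 2/6 = 33.3% (above).

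**4. Strength of a small-cohort ORR.** Inputs: 3 or 6 subjects at escalation review (Synopsis, Protocol 4.3.2); average of 4 per level (Protocol 10.1). Let r be the smallest count with r/n ≥ 0.30. At a true response rate p, the chance of passing the ORR limb is P(X ≥ r), X ~ Binomial(n, p). At p = 0.19:

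- n = 3, r = 1: 1 − 0.81³ = 0.469
- n = 4, r = 2 (1/4 = 25% fails): 1 − 0.81⁴ − 4(0.19)(0.81³) = 0.166
- n = 6, r = 2: 1 − 0.81⁶ − 6(0.19)(0.81⁵) = 0.320

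| n | r | P(pass), true 19% | P(pass), true 30% | Exact 95% CI at r/n |
|---|---|---|---|---|
| 3 | 1 | 0.469 | 0.657 | 0.8–90.6% |
| 4 | 2 | 0.166 | 0.348 | 6.8–93.2% |
| 6 | 2 | 0.320 | 0.580 | 4.3–77.7% |

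Every interval contains 19%. These probabilities concern the ORR limb alone; the full rule also requires the DLT and trough limbs and so is passed less often.

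**5. Adding expansion subjects.** An escalation cohort of 3 or 6 plus a full expansion of 12 gives 15 or 18 at the selected dose. The smallest passing results have exact intervals of 11.8–61.6% (5/15) and 13.3–59.0% (6/18): still wide, but much more informative than the escalation cohort alone.

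**The case against.** The strongest reply is that the SAP does not choose the dose. The SRC does, during the study, with subject-level data. SAP 8.6.2.1 lists all tumor assessments by subject, and SAP 8.5 lists dosing by subject and plots treatment duration by dose cohort, so dose-level response can be rebuilt. Table shells and the PK and pharmacodynamic plans are in separate documents not available here. A subject at X can move up only after X+1 is declared safe, so the first review of X comes before any of its subjects escalate. Efficacy is secondary, and SAP 7.9 calls the study exploratory.

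Most of this stands, and it limits the point. A reader might infer that the planned tables would select the wrong dose, or that dose-level response is lost. Neither follows: the gap is in the summaries, not in the decision process or the data. The sequencing argument protects the first review of X, but not the final report or later looks, which include responses and adverse events from subsequent cycles. Being exploratory explains the absence of multiplicity control; it does not explain omitting a descriptive estimate that a primary objective calls for.

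A reader might also infer that some ineffective dose is almost certain to pass. With four independent cohorts of the planning average, all at 19%, at least one passes the ORR limb with probability 1 − (1 − 0.166)⁴ ≈ 0.52. The documents do not say how many cohorts would meet the other limbs. They also apply 30% to a dose, never to a pooled rate, so an invented pooled example decides nothing.

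**Conclusion.** The point holds as a reporting gap. The mBED's activity criterion is defined for a dose and sought on each schedule, while every ORR, DOR and PFS summary the SAP describes pools doses and schedules, so none can verify the SRC's choice. The starting-dose rule already affects the by-cohort adverse event tables and would affect ORR once split, where a single response can carry a cohort of 6 across 30%. At a true 19% the ORR limb is passed with probability 0.47, 0.17 or 0.32 at n = 3, 4 or 6. These figures assume independent subjects with a common response rate and take the historical 19% as that rate.

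It may be tempting to go further, open the expansion on DLT and trough alone, and judge ORR at 6 or more of 18. The documents do not support that. It would rewrite the protocol's dose-selection rule, 18 subjects are not assured (a cohort may clear with 3, and the expansion is up to 12), and the rule passes with probability only 0.47 at a true 30%, against 0.11 at 19%.

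**What to change.** - **SAP 7.7 and 8.6.2.1:** add a descriptive table of AML combination ORR with exact 95% intervals by schedule and dose cohort. Add a row for escalation plus expansion subjects at the selected dose on each schedule.
- **SAP 7.6:** for dose-level ORR, count responses reached before any within-subject dose increase and show later responses separately. Keep the by-cohort adverse event tables and add a display by dose at onset.
- **SAP Table 3-3:** it lists a single IS3w,1w cohort, numbered 20, where the protocol has Cohorts 21–25. Bring the table into line so that the new rows match the protocol.

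The cost is a few more tables, with small cells and wide intervals that should be labelled descriptive. No extra subjects are needed, and the escalation and expansion rules stay as written.
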